10.4.3 Assessment of Biomarkers

Blood samples will be collected from all participants in this study prior to dosing on day 1 and at days 2, 3, and 4. These samples will be used to test for biomarkers involved in the inflammatory process and in the autonomic nervous system, including the inflammatory panel (IFN γ , IL1 β , IL2, IL4, IL6, IL8, IL10, IL13, and TNF α), Catecholamines (Epinephrine, norepinephrine and dopamine) and hsCRP.

Descriptive statistics and graphs will be presented by treatment group for each biomarker of the following:

- Biomarker concentration at baseline and each timepoint post treatment
- Change from baseline (CFB) in biomarker concentration.

Exploratory analysis of biomarker concentration and their CFB following treatment will be conducted in correlation with the observed clinical response to study treatment.

11.0 Safety Analyses

The safety analysis will be performed using the safety population. The safety parameters will include adverse events (AEs), physical examinations, clinical laboratory test results, vital sign

measurements, electrocardiograph (ECG) results, and pulmonary function testing. For each of the physical examinations, clinical laboratory test results, vital sign measurements, and ECG parameters, the last non-missing safety assessment before the study treatment will be used as the baseline for all analyses of that safety parameter. Continuous variables will be summarized by number of participants and mean, SD, first quartile (Q1), median, minimum, third quartile (Q3), and maximum values. Categorical variables will be summarized by number and percentage of participants.

11.1 Adverse Events

Adverse events will be coded by system organ class and preferred term using the Medical Dictionary for Regulatory Activities (MedDRA).

An AE will be considered a treatment-emergent adverse event (TEAE) if the AE began or worsened (increased in severity or became serious) on or after the date/time of the study injection. Per case report form instructions, a new AE record will be created with a new AE onset date/time for any AE that worsens. Therefore, TEAEs can simply be identified as those AEs with recorded onset date/time on or after the date/time of the study injection.

The number and percentage of participants reporting TEAEs in each study treatment group will be tabulated by descending percentage of the total across treatment groups, by system organ class and preferred term, and further categorized by severity and relationship to the study treatment. If more than 1 TEAE is coded to the same preferred term for the same participant, the participant will be counted only once for that preferred term. For tables presented by severity, the greatest severity observed will be used.

The number and percentage of participants who have treatment-emergent serious adverse events (TESAE) will be summarized by system organ class, preferred term and treatment group. A similar summary will be presented for subjects with TEAEs leading to discontinuation from the study. In addition, separate subject listings will be generated for deaths, serious adverse events (SAEs), and TEAEs leading to study discontinuation.

Cardiovascular events of interest in this study are: heart failure or congestive heart failure, stroke or transient ischemic attack, myocardial infarction, renal failure, respiratory failure, ventricular arrhythmias, and supraventricular arrhythmias. The number and percentage of participants who have treatment-emergent cardiovascular event of interest will be presented by treatment group. The list of preferred terms within each of the cardiovascular events of interest is provided below:

Heart failure or Congestive heart fa	nure	
Cardiac failure	Acute right ventricular failure	Acute pulmonary oedema
Cardiac failure acute	Chronic left ventricular failure	Pulmonary oedema
Cardiac failure chronic	Chronic right ventricular failure	Cor pulmonale
Cardiac failure congestive	Left ventricular failure	Cor pulmonale acute
Cardiac failure high output	Right ventricular failure	Cor pulmonale chronic
Cardiopulmonary failure	Ventricular failure	Low cardiac output syndrome
Acute left ventricular failure	Cardiogenic shock	
Stroke or Transient ischemic attack		
Cerebrovascular accident	Vertebrobasilar stroke	Cerebral cyst haemorrhage
Cerebral infarction	Basilar artery thrombosis	Cerebral haemorrhage
Embolic cerebral infarction	Brain stem embolism	Cerebral microhaemorrhage
Thrombotic cerebral infarction	Brain stem thrombosis	Epidural haemorrhage
Cerebellar infarction	Cavernous sinus thrombosis	Extra-axial haemorrhage
Haemorrhagic infarction	Cerebellar artery thrombosis	Haemorrhage intracranial
Haemorrhagic cerebral infarction	Cerebellar embolism	Intracranial tumour haemorrhage
Ischaemic cerebral infarction	Cerebral artery embolism	Intraventricular haemorrhage
Infarction	Cerebral artery thrombosis	Meningorrhagia
Lacunar infarction	Cerebral gas embolism	Pituitary haemorrhage
Basal ganglia infarction	Cerebral microembolism	Subarachnoid haemorrhage
Basal ganglia stroke	Cerebral thrombosis	Subdural haemorrhage
Brain stem infarction	Cerebral venous thrombosis	Thalamus haemorrhage
Brain stem stroke	Intracranial venous sinus thrombosis	Traumatic intracranial haemorrhage
Cerebellar stroke	Precerebral artery thrombosis	Transient ischaemic attack
Embolic stroke	Superior sagittal sinus thrombosis	Brain stem ischaemia
Haemorrhagic stroke	Transverse sinus thrombosis	Cerebral ischaemia
Haemorrhagic transformation stroke	Vertebral artery thrombosis	Cerebellar ischaemia
Ischaemic stroke	Basal ganglia haemorrhage	Cerebral small vessel ischaemic
Lacunar stroke	Brain stem haemorrhage	disease
Cerebral septic infarct	Brain stem microhaemorrhage	Reversible ischaemic neurological
Thalamic infarction	Central nervous system haemorrhage	deficit
Post procedural stroke	Cerebellar haemorrhage	Delayed ischaemic neurological
Pseudostroke	Cerebellar microhaemorrhage	deficit
Stroke in evolution	Cerebral arteriovenous malformation	
Thrombotic stroke	haemorrhagic	
Myocardial infarction		
Acute myocardial infarction	Post procedural myocardial	Myocardial necrosis
ECG signs of myocardial infarction	infarction	Myocardial ischaemia
Myocardial infarction	Silent myocardial infarction	Subendocardial ischaemia
Periprocedural myocardial infarction	Papillary muscle infarction	
Renal failure	1 5	I
Donal failura	Destronal failure	A auto bide au inime
Kenal lanure	rostrenal failure	Acute kloney injury

 Table 11–1
 Cardiovascular Adverse Events of Interest

Hepatorenal failure	Prerenal failure	Chronic kidney disease
Postoperative renal failure		
Ventricular arrhythmias		
Ventricular arrhythmia	Parasystole	Ventricular parasystole
Ventricular tachyarrhythmia	Rhythm idioventricular	Ventricular pre-excitation
Arrhythmia	Tachyarrhythmia	Ventricular tachycardia
Accelerated idioventricular rhythm	Torsade de pointes	Anomalous atrioventricular
Cardiac fibrillation	Ventricular extrasystoles	excitation
Cardiac flutter	Ventricular fibrillation	Ventricular asystole
Extrasystoles	Ventricular flutter	
Supraventricular arrhythmias		
Arrhythmia supraventricular	Sinus tachycardia	Nodal arrhythmia
Atrial fibrillation	Supraventricular extrasystoles	Nodal rhythm
Atrial flutter	Supraventricular tachyarrhythmia	Sinus arrest
Atrial parasystole	Supraventricular tachycardia	Sinus arrhythmia
Atrial tachycardia	Paroxysmal arrhythmia	Sinus bradycardia
Junctional ectopic tachycardia	Bradyarrhythmia	Sinus node dysfunction

To assess possible distant spread of toxin (PDSOT), 40 MedDRA preferred terms that may be associated with botulinum toxin effects have been identified. All TEAEs associated with PDSOT will be tabulated by SOC, preferred term and treatment group; in addition, all PDSOT TEAEs will be listed by subject. The 40 terms are listed below.

Cardiac Disorders	Nervous System Disorders
Bradycardia	Bell's palsy
	Bulbar palsy
Eye Disorders	Cranial nerve palsies multiple
Accommodation disorder	Cranial nerve paralysis
Diplopia	Dysarthria
Opthalmoplegia	Facial paralysis
Eyelid function disorder	Facial paresis
Eyelid ptosis	Hyporeflexia
Pupillary reflex impaired	Hypotonia
Vision blurred	Paralysis
	Paresis cranial nerve
Gastrointestinal Disorders	Peripheral nerve palsy
Constipation	Peripheral paralysis
Dry mouth	Speech disorder
Dysphagia	Vocal cord paralysis
Ileus paralytic	Vocal cord paresis
Infections and Infestations	Renal and Urinary Disorders
Botulism	Urinary retention
Musculoskeletal and Connective Tissue	Respiratory, Thoracic and Mediastinal Disorders
Disorders	Aspiration
Muscular weakness	Diaphragmatic paralysis
	Dysphonia
	Dyspnoea
	Pneumonia aspiration
	Respiratory arrest
	Respiratory depression
	Respiratory failure
	Reproductive System and Breast Disorders
	Pelvic floor muscle weakness

MedDRA Preferred Terms Evaluated for Possible Distant Spread of Toxin

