#### Events NOT Meeting the AE Definition

- Any clinically significant abnormal laboratory findings or other abnormal safety assessments that are associated with the underlying disease, unless judged by the investigator to be more severe than expected for the participant's condition. Merely repeating an abnormal test, in the absence of any of the above conditions, does not constitute an AE. Any abnormal test result that is determined to be an error does not require recording as an AE.
- The disease/disorder being studied or expected progression, signs, or symptoms (clearly defined) of the disease/disorder being studied, unless more severe than expected for the participant's condition
- Medical or surgical procedure (eg, endoscopy, appendectomy): the condition that leads to the procedure is the AE
- Situations in which an untoward medical occurrence did not occur (social and/or convenience admission to a hospital)
- Anticipated day-to-day fluctuations of pre-existing disease(s) or condition(s) present or detected at the start of the study that do not worsen

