Concurrent procedures will be presented in a listing. A tabulation will be provided for concurrent procedures performed due to atrial fibrillation or atrial flutter. Concurrent procedures performed

due to atrial fibrillation or atrial flutter may include: alcohol septal ablation, cardiac ablation, cardioversion, and additional cardiac surgery. See Section 10.3 below for additional discussion of concurrent procedures performed due to atrial fibrillation or atrial flutter.

Additional medications or concurrent procedures meeting the classifications above may be added at the discretion of the clinical team prior to the interim database lock for the primary analysis.

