10.1 Primary Efficacy Variable

For primary efficacy consideration, POAF will be defined as any continuous episode of AF lasting 30 seconds or more during the first 30 days post-surgery. The primary efficacy variable is the percentage of participants with at least 1 continuous AF episode \geq 30 seconds during the first 30 days post-surgery.

For each of the AGN-151607 doses of 125 U and 250 U, the null hypothesis is that there is no difference between that dose group and placebo in the percentage of participants with at least 1 continuous AF episode \geq 30 seconds during the first 30 days post-surgery. The alternative hypothesis is that there is a difference between the AGN-151607 dose group under consideration and placebo.

The proportion of participants with at least 1 continuous AF episode \geq 30 seconds during the first 30 days post-surgery will be presented for each treatment group. Between-group comparisons will be performed using the Cochran-Mantel-Haenszel (CMH) test for general association stratified by type of surgery (presence or absence of valve surgery) and age group (< 65 or \geq 65 years). P-values, adjusted Mantel-Haenszel (MH) odds ratios and relative risks (and their corresponding 95% confidence intervals) will be presented for each comparison of AGN-151607 versus placebo. Exact (Clopper-Pearson) 95% confidence intervals of the observed proportion will be presented for each treatment group. In addition, exact unconditional 95% confidence interval (using the score method) for the difference in observed proportion between each AGN-151607 dose group versus placebo will also be presented.

For the primary efficacy variable, supplementary analyses will be performed based on the Supplementary ePatch Analysis Sets (SEA-7 and SEA-30) and the Beta Blocking Agent Withdrawn ePatch Analysis Set. The supplementary analyses will use the same methods described for the primary analysis.

For the primary efficacy variable, subgroup analyses will be performed using the same methods described for the primary analysis based on the correct stratification group (with the other stratification factor used for the stratified CMH test):

- type of surgery (presence or absence of valve surgery)
- age group (< 65 or \geq 65 years)]

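### SAP Table 11-1 counts AF and bradyarrhythmia in one safety category, so a fall in AF recorded as adverse events can offset a rise in bradyarrhythmia in that summary

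*SAP*

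**What the plan says.** SAP 11.1 names seven groups of cardiovascular events of interest. The end of that list and the reporting rule read "ventricular arrhythmias, and supraventricular arrhythmias. The number and percentage of participants who have treatment-emergent cardiovascular event of interest will be presented by treatment group". Table 11-1 gives the preferred terms in each group. Under supraventricular arrhythmias it places Atrial fibrillation, Atrial flutter and Atrial tachycardia alongside Bradyarrhythmia, Sinus bradycardia, Sinus arrest, Sinus node dysfunction and Nodal rhythm. One row of the table reads "Junctional ectopic tachycardia Bradyarrhythmia Sinus node dysfunction".

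AF is also what the treatment is meant to prevent. SAP 10.1 says "The primary efficacy variable is the percentage of participants with at least 1 continuous AF episode" of at least 30 seconds in the first 30 days, and SAP 10.0 takes AF to mean fibrillation or flutter.

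Four other places bear on the point:

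- The list of possible distant spread of toxin (PDSOT) terms in SAP 11.1 contains Bradycardia. Sinus bradycardia is only in Table 11-1. Atrioventricular block appears in neither list, although Protocol 5.2 excludes recent symptomatic block above first degree.
- SAP 8.0 says "Concurrent procedures will be presented in a listing". A table is planned only for procedures performed because of AF or flutter.
- Protocol 10.3 lists among events that are not adverse events "The disease/disorder being studied or expected progression, signs, or symptoms (clearly defined) of the disease/disorder being studied, unless more severe than expected". It also says that lack of efficacy in itself is not reported as an adverse event.
- SAP 11.1 also tabulates all treatment-emergent events by system organ class and preferred term in each arm.

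**The concern.** One participant count adds an intended benefit to a possible harm. The injections act on cardiac autonomic ganglia, and the SAP itself treats Bradycardia as a possible toxin effect. If AF falls by the planned 20 points and those AF events reach the adverse-event database, the category percentage can be lower on active treatment while bradyarrhythmia is more frequent. A reader of the cardiac safety table could take that as reassurance.

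No other planned output counts participants with any bradyarrhythmia. The relevant terms are spread over several rows and two lists, and conduction block is in neither list.

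**Working it through.** **The plan's own figure.** The documents give no figure for this safety category. Their only relevant calculation is the sample size (Protocol 9.2, SAP 13.0), which supplies the AF rates: 47.8% on placebo, 27.8% on each dose, 100 per arm, two-sided 0.05, power about 80%.

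- Mean rate 0.378. Null SE = √(2 × 0.378 × 0.622 / 100) = 0.0686. Alternative SE = √((0.478 × 0.522 + 0.278 × 0.722) / 100) = 0.0671.
- Without continuity correction: Φ((0.200 − 1.96 × 0.0686) / 0.0671) = 83.6%.
- With continuity correction (subtract 1/100): 79.6%. This matches the stated figure.

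**Inputs for the category.**

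- AF, plan effect: 47.8% to 27.8%.
- AF, smaller effect, from the 130-participant trial described in Protocol Section 2: 47.8% to 36.5%.
- Background bradyarrhythmia rate b: not in the documents. Assumed range 2% to 20%.
- Independence of AF and bradyarrhythmia: assumed.

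**Formula.** Pooled rate = 1 − (1 − AF)(1 − bradyarrhythmia). For example, 5% rising to 15% gives placebo 1 − 0.522 × 0.95 = 50.4% and active 1 − 0.722 × 0.85 = 38.6%.

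Plan AF effect, all AF recorded as adverse events:

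| Background b | Placebo | Active, b doubled | Active, b tripled |
|---|---|---|---|
| 2% | 48.8% | 30.7% | 32.1% |
| 5% | 50.4% | 35.0% | 38.6% |
| 10% | 53.0% | 42.2% | 49.5% |
| 15% | 55.6% | 49.5% | 60.3% |
| 20% | 58.2% | 56.7% | 71.1% |

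**Limit of masking.** A k-fold rise is hidden (active pooled rate no higher than placebo) when b ≤ (AF placebo − AF active) / [k(1 − AF active) − (1 − AF placebo)].

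| AF recorded as AE | Doubling hidden up to | Tripling hidden up to |
|---|---|---|
| All, 47.8% vs 27.8% | 0.200/0.922 = 21.7% | 0.200/1.644 = 12.2% |
| All, 47.8% vs 36.5% | 0.113/0.748 = 15.1% | 0.113/1.383 = 8.2% |
| Half, 23.9% vs 13.9% | 0.100/0.961 = 10.4% | 0.100/1.822 = 5.5% |
| None | no masking | no masking |

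**Dependence on how much AF is recorded.** Let c be the share of AF participants with an AF adverse event, and take bradyarrhythmia at 5% versus 15%. The pooled rates are equal when 0.95(1 − 0.478c) = 0.85(1 − 0.278c), so c = 0.100/0.2178 = 46%. With 36.5% in place of 27.8%, c = 0.100/0.14385 = 70%. Below these shares the active arm shows the higher rate. At c = 25% with the plan effect it is 16.4% on placebo versus 20.9% on active.

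**Dependence on independence.** At 5% versus 15% with all plan-rate AF recorded, no overlap gives 52.8% versus 42.8%, and full overlap gives 47.8% versus 27.8%. The direction is the same. Other terms in the category, if independent and equally frequent in both arms, multiply both complements by the same factor and leave the limits unchanged.

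**What a separate count would show.** With 110 per arm and a two-sided 0.05 comparison, 5% versus 15% is detected about 70% of the time, and 5% versus 10% about 29%.

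**The case against.** The strongest objection is that the calculation takes every patch-detected AF endpoint as an adverse event, while Protocol 10.3 restricts exactly that. The 47.8% and 27.8% are incidence assumptions for any 30-second episode, not adverse-event rates. This stands: the masking is conditional on how much AF is recorded, and that share is unknown. It does not remove the point, because Table 11-1 lists AF and flutter and so expects some to be recorded. If sites read the rule differently, the category is also hard to interpret.

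A reader might go further and infer that the safety plan as a whole cannot show a bradyarrhythmia increase. The documents do not support that. By arm, the plan has:

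- treatment-emergent and serious events by preferred term, and Bradycardia in the PDSOT table (SAP 11.1);
- low pulse, at most 50 bpm with a fall of at least 15 (SAP 11.3);
- heart rate and PR interval with change from baseline, and a count of PR of 230 msec or more (SAP 11.4).

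Protocol 9.4.2.4 adds a display of clinically significant ECG abnormalities, and SAP 12.0 plans four DSMB reviews. The condition leading to a pacemaker is itself the adverse event under Protocol 10.3, so it should reach the event tables even if the procedure is only listed. All of this stands and confines the masking to the category summary. None of it is a grouped count, however, and the ECG criteria in Table 11-4 have no low heart-rate limit.

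Table layouts are in a separate document, so preferred-term rows may sit beneath the category. That would soften the problem but would still give no bradyarrhythmia total.

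**Conclusion.** The point holds as a conditional flaw in one pre-specified safety summary. Table 11-1 adds the efficacy outcome to a possible harm. If all AF is recorded as adverse events at the plan's rates, with independence, the category hides a doubling of bradyarrhythmia up to a background of about 22% and a tripling up to about 12%. With the smaller cited AF effect the limits are about 15% and 8%; with half of plan-rate AF recorded, about 10% and 5.5%. With no AF recorded there is no masking.

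A reader might infer that any doubling or tripling would be hidden. That does not follow: the documents give no background rate, and above these limits the rise shows even in the pooled row. The finding concerns reporting only and does not touch the efficacy inference, the sample size or the data collected.

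**What to change.** 1. In Table 11-1, split the category in two, each counted by participant and arm: (a) AF, flutter and other supraventricular tachyarrhythmia; (b) bradyarrhythmia and conduction disorder, holding Bradycardia, Sinus bradycardia, Bradyarrhythmia, Sinus arrest, Sinus node dysfunction, the nodal rhythm terms and the atrioventricular block terms. Bradycardia can stay in the PDSOT list as well.
2. Tabulate new pacemaker implantation for any reason by arm, from the concurrent-procedure data already collected.
3. Reconcile Protocol 10.3 with Table 11-1 on whether AF is recorded as an adverse event, and state the rule used in the analysis.

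The cost is one regrouped table, one extra table and a short clarification, with no new procedures or data. It is best done before the lock for the interim/primary analysis, when SAP 12.0 unblinds the sponsor's study personnel. The split removes the offset but does not make the trial sensitive to small increases: a doubling from 5% to 10% would still be detected only about 29% of the time.

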11.2 Clinical Laboratory Parameters

Descriptive statistics for clinical laboratory values (in SI units) and changes from the baseline values at each assessment time point will be presented by visit and treatment group for all continuous laboratory parameters. Categorical laboratory parameters will be presented in listings. The laboratory parameters are:

Hematology: Basophils absolute cell count, eosinophils absolute cell count, hematocrit, hemoglobin, lymphocytes absolute cell count, monocytes absolute cell count, neutrophil absolute cell count, mean corpuscular hemoglobin (MCH), mean corpuscular hemoglobin concentration (MCHC), mean corpuscular volume (MCV), platelet count, percentage reticulocytes, red blood cell (RBC) count, and white blood cell (WBC) count.

Chemistry:	Albumin, alanine aminotransferase (ALT), alkaline phosphatase, aspartate aminotransferase (AST), direct bilirubin, indirect bilirubin, total bilirubin, blood urea nitrogen (BUN), calcium, chloride, total cholesterol, creatinine, estimated glomerular filtration rate (eGFR), glucose non-fasting, triglycerides, HDL, LDL, Hemoglobin A1c, potassium, total protein, and sodium.
Urinalysis:	Bilirubin, blood, glucose, ketones, leukocyte esterase, nitrite, pH, protein, specific gravity, urobilinogen, and microscopic examination (if blood or protein is abnormal)
Coagulation:	Prothrombin time (PT), activated partial thromboplastin time (aPTT), and thrombin time (TT).

Clinical laboratory test values will be considered potentially clinically significant (PCS) if they meet either the lower-limit or higher-limit PCS criteria listed in Table 11–2. The number and percentage of participants who have PCS postbaseline clinical laboratory values will be tabulated by treatment group at each assessment. The percentages will be calculated relative to the number of participants with available non-PCS baseline values and at least 1 postbaseline assessment. The numerator will be the total number of participants with available non-PCS baseline values and at least 1 PCS postbaseline value. A supportive listing of participants with PCS postbaseline values will be provided, including the PID number, baseline and all postbaseline (including non-PCS) values.

Shift tables from baseline to each post-baseline visit for clinical laboratory parameters will be presented by treatment group for the following categories: low, normal, and high, which are provided by lab vendor.

Table 11–2	Criteria for Potentially Clinically Significant Laboratory Results
------------	--

Parameter	SI Unit	Lower Limit	Higher Limit	
CHEMISTRY				
Albumin	g/L	$< 0.9 \times LLN$	> 1.1 × ULN	
Alanine aminotransferase	U/L	—	\geq 3 × ULN	
Alkaline phosphatase	U/L	—	\geq 3 × ULN	
Aspartate aminotransferase	U/L	—	\geq 3 × ULN	
Bilirubin, total	µmol/L	—	> 1.5 × ULN	
Calcium	mmol/L	< 0.9 × LLN	> 1.1 × ULN	
Chloride	mmol/L	$< 0.9 \times LLN$	> 1.1 × ULN	
Cholesterol	mmol/L	—	> 1.3 × ULN	
Creatinine	µmol/L	—	> 1.3 × ULN	
Glucose, fasting	mmol/L	$< 0.8 \times LLN$	> 1.2 × ULN	
Glucose, nonfasting	mmol/L	$< 0.8 \times LLN$	> 1.4 × ULN	
Potassium	mmol/L	$< 0.9 \times LLN$	> 1.1 × ULN	
Protein, total	g/L	< 0.9 × LLN	> 1.1 × ULN	
Sodium	mmol/L	$< 0.9 \times LLN$	> 1.1 × ULN	
Triglycerides	mmol/L	—	$> 2 \times ULN$	
Urea nitrogen	mmol/L	—	> 1.2 × ULN	
Uric acid	µmol/L	—	> 1.2 × ULN	
HEMATOLOGY				
Basophils, absolute cell count	10 ⁹ /L	—	$> 3 \times ULN$	
Neutrophils, absolute cell count	10 ⁹ /L	$< 0.8 \times LLN$	> 1.5 × ULN	
Hematocrit	Ratio	$< 0.9 \times LLN$	> 1.1 × ULN	
Hemoglobin	g/L	$< 0.9 \times LLN$	> 1.1 × ULN	
Platelet count	10 ⁹ /L	$\leq 0.5 \times LLN$	$\geq 1.5 \times \text{ULN}$	
Red blood cell count	10 ¹² /L	$< 0.9 \times LLN$	> 1.1 × ULN	
White blood cell count	10 ⁹ /L	$\leq 0.7 \times LLN$	\geq 1.5 × ULN	
URINALYSIS				
pH		$< 0.9 \times LLN$	> 1.1 × ULN	
Specific gravity		_	> 1.1 × ULN	

LLN = lower limit of normal value provided by the laboratory; SI = *Le Système International d'Unités* (International System of Units); ULN = upper limit of normal value provided by the laboratory.

